2. STUDY OBJECTIVES

The main objective of this study is to generate real-world evidence reflecting the experience of individuals with exocrine pancreatic insufficiency (EPI) due to chronic pancreatitis (CP). Efforts will be directed toward understanding the unmet need and therapeutic burden to identify the most critical factors that influence treatment choices/prescribing patterns, quality of life, and healthcare utilization outcomes in standard of care for individuals with EPI due to CP. This study has the following specific aims:

1. Create a cohort of well-characterized patients with EPI due to CP for participation in retrospective and prospective research
2. Collect clinical data to characterize both the EPI due to CP disease history and disease progression through a combination of retrospective and prospective collection of medical history, comorbidities, and treatment approaches aimed at increasing the level of understanding of a heterogeneous condition such as EPI
3. Collect data on the differing clinical care practices for patients with EPI to better understand the impact of those patterns on outcomes (including quality of life, comorbidities, and treatments)

4. Collect data on treatment compliance that may impact the EPI due to CP disease experience and/or outcome
5. Collect baseline and longitudinal participant-reported outcome (PRO) data on abdominal pain, GI symptoms, dietary habits, health-related quality of life, depression/anxiety, and PERT use and treatment satisfaction to evaluate the impact of EPI on individuals' health and daily life
6. Gather data on healthcare utilization to be combined with clinical data to generate evidence for the impact and burden of EPI due to CP in this cohort on the healthcare system.

3. STUDY DESIGN

This is a prospective, non-interventional study for individuals with EPI due to CP who are under the care of a gastroenterologist. Longitudinal data will be collected from both study participants as well as from their clinical encounters with their treating gastroenterology providers using a structured and standardized data collection method. The scope of data collection (see [Schedule of Assessments](#)) from the study participants includes demographics, current work status, current insurance coverage, family disease history, weight/height, current over the counter (OTC) herbal/nutritional supplements, healthcare utilization, and PROs on abdominal pain, GI symptoms, dietary habits, health-related quality of life, depression/anxiety, and PERT use and treatment satisfaction. At the time of routine clinical encounters, Investigators complete assessments on medical history, information on suspected/confirmed EPI diagnosis, CP etiology, clinical manifestations of EPI (GI and nutritional manifestations), AEs, and current treatment(s).

3.1 Study Plan and Duration

Target enrollment is approximately 400 study participants with suspected or confirmed EPI. Approximately 20 clinical gastroenterology sites in the United States will be contracted to participate.

3.2 Study Duration

This is a 5-year study with an anticipated first enrollment date of 01 April 2021. The total enrollment period will be 24 months in length and data collection and study close-out will take place 3 months prior to the anticipated study end date. The study duration from enrollment to study end is five (5) years.

4. SITE SELECTION

4.1 Investigator Qualifications

Investigators will be selected after review of required qualifications and available resources. Investigators will be selected based on a number of criteria (e.g., practice setting, practice geographical location, number of EPI patients seen per month, type of IRB, etc.) to ensure that a representative sample of sites will be included in the study. A qualified Investigator is entitled to provide health care under the laws of the state where the registry site is located and for the purposes of this study must also be a licensed board eligible or board-certified gastroenterologist, or an advanced practice provider (i.e., certified nurse practitioner, physician assistant, gastroenterology resident or fellow) working at a gastroenterology practice and in good standing with a professional medical association. The Investigator is responsible for validating all information in the defined study schedule. If the study is conducted by a team of individuals at a site, the Investigator will need to complete a delegation of authority log for the registry. Each qualified physician at a site is assigned a unique ID to use when collecting and providing data for the registry. The Investigator will be asked to complete an assessment on provider demographics (e.g., age, gender, years in practice, number of EPI patients per month) and other site metrics (e.g., specialty, practice setting, practice type, and geographical location).

4.2 Study-Specific Training for Investigators and Support Staff

Study-specific training must be completed by Investigators, Sub-Investigators, and all support staff at each participating registry site prior to the initiation of study participant enrollment and data collection. Required training presentations and assessments (if applicable) are provided by HealthiVibe via teleconference and/or videoconference sessions prior to enrollment. The registry site training will be documented in a training log, which will capture the site staff that completed the trainings along with confirmation that the training content was understood.

5. STUDY POPULATION

5.1 Study Participant Selection Criteria

To be eligible for the registry, study participants must meet all [inclusion criteria](#) and none of the [exclusion criteria](#) below.

5.2 Inclusion Criteria

To be eligible for enrollment, a study participant must meet the inclusion criteria below:

1. At least 18 years of age (or age of majority)
2. Willing to provide consent to participate
3. Meet ONE (1) of the following at the time of enrollment:
 - a. Diagnosis of chronic pancreatitis (CP)
 - b. Diagnosis of recurrent acute pancreatitis (RAP)
4. Suspected or confirmed diagnosis of EPI made by a healthcare provider
5. On PERT, either prior to the Enrollment Visit or newly prescribed at the time of the Enrollment Visit.

5.3 Exclusion Criteria

To be eligible for enrollment into the registry, a study participant must not have any of the criteria below:

1. Currently participating in or planning to participate in a double-blind randomized trial and/or open-label Phase 3b/4 on CP or EPI
2. Diagnosed with any of the following conditions at the time of enrollment:
 - a. Cystic fibrosis
 - b. Fibrosing colonopathy
 - c. A history of or current diagnosis of pancreatic cancer, main duct papillary mucinous neoplasms (IPMNs), and other pancreatic malignancies
 - d. Allergy to pork or other porcine pancreatic enzyme products (PEPs)
 - e. Any condition that would, in the investigator's opinion, limit the individual's ability to complete the study.

6. STUDY PROCEDURES

6.1 Schedule of Assessments

The registry activities are summarized in the schedule of assessments outlined in **Table 1**.

Table 1. Schedule of Assessments

	Enrollment Day 0	Follow-up direct from study participant ± 7 days		Follow-up on-site (Clinical encounter)	Study participant exit [‡] May occur any time; max. data collection period is 5 years
		Every 3 months	Every 6 months		
Study Participant Provided Data[§]					
Informed consent	X				
Demographic information	X				
Family disease history	X				
Training for remote assessment completion	X				
Height	X				
Weight	X	X			
Current Insurance/work status	X	X			
Current OTC nutritional/herbal supplements	X	X			
Abdominal pain	X	X			
GI symptoms	X	X			
PERT use and treatment satisfaction	X	X			
Dietary habits	X		X		
Health-related quality of life	X		X		
Anxiety/depression	X		X		
Healthcare utilization	X		X		
Investigator Provided Data[*]					
Review/confirm participant eligibility	X				
EPI diagnosis	X				
CP etiology	X				
Medical history	X				
EPI clinical manifestations	X			X	
AEs [•]				X	
Current treatment(s)	X			X	
Reason for exit					X

[§] Study participant provided data will be collected remotely via EDC portal.

^{*} Investigator provided data will be provided during clinical encounters at the registry site. Every 180 days ±30 days with minimum 150 days between visits unless follow-up visit meets criteria for EARLY On-Site Follow-Up (see section 6.3.2)

[‡] Occurs if data collection period has ended or if study participant exits the study due to death, is LTFU, transfers to another gastroenterologist, withdraws from the study or being terminated by the Investigator.

[•] The Investigator will provide information about the occurrence and seriousness of AEs at Follow-up. In the event that an AE is serious, the Investigator will complete an SAE form.

6.2 Enrollment

6.2.1 Informed Consent

Study participants will be enrolled when all of their questions about the study have been addressed, they have signed the informed consent form (ICF) and have met all of the inclusion criteria and none of the exclusion criteria (see [Study Participant Selection Criteria](#)). Informed consent will be obtained either via paper and/or electronic consent.

Once the participant's consent is obtained, a unique study participant identifier will be assigned that will be used to collect the participant's data throughout the study.

6.2.2 Clinical Data Points

During the Enrollment visit, the following information will be collected from the study participant:

- Demographics (i.e., age, gender, ethnicity, race, marital status, highest level of education, annual household income, residence setting, and zip code)
- Current insurance coverage and current work status
- Height/weight (current weight, highest weight ever, unintentional weight loss)
- Family history of pancreatic disease, pancreatic cancer, pancreatic resection, celiac disease, and diabetes
- Current OTC herbal/nutritional supplements
- Abdominal pain, GI symptoms, dietary habits, health-related quality of life, depression/anxiety, PERT use and treatment satisfaction, and healthcare utilization.

The following assessments will be collected during the clinical encounters with the Investigator:

- EPI-related information including EPI diagnosis, date of onset of symptoms indicative of EPI, method of confirmed/suspected EPI diagnosis (i.e., abnormal fecal elastase FE-1 test, clinical steatorrhea, vitamin deficiency, weight loss, pancreatic function testing, and/or other), CP etiology following the Toxic-metabolic, Idiopathic, Genetic, Autoimmune, Recurrent and severe acute pancreatitis and Obstructive (TIGAR-O) v2.0 classification (Whitcomb, 2019), and clinical manifestations of EPI (i.e., GI manifestations such as diarrhea/loose stool, steatorrhea, abdominal pain, bloating; nutritional manifestations such as unintentional weight loss/difficulty gaining weight, malnutrition, vitamin D and other vitamin/mineral deficiencies, and other)
- Medical history (history of comorbidities and surgical/endoscopic procedures, laboratory abnormalities)
- Current treatment(s) including medication (i.e., PERT and others) and other therapies, such as nutritional support, cognitive-behavioral therapy, as well as response to therapy.

6.3 Follow-Up

At Follow-Up, data will be collected from the study participant through remote data collection and by the Investigator at on-site clinical encounters. Study procedures for Follow-Up will be described in the sections below.

6.3.1 Direct From Study Participant Follow-Up

The study participant will complete assessments remotely via EDC portal, accessed via a mobile-friendly secure web URL every 3 months.

Autogenerated reminders via email or text (depending on study participant preference) will be sent weekly starting 3 weeks prior to the scheduled data collection date. If the study participant does not complete their assessments through the EDC portal within 7 days of the scheduled date, reminders will be sent to the study participant every other day. If the participant has not completed the assessments 21 days after the scheduled data collection date, the HealthiVibe Registry Manager will call the study participant to remind them to complete the assessments and/or find out about the reason for the delay.

6.3.2 On-Site Follow-Up Visit

Routine clinical encounters are performed approximately every 6 months or sooner if a study participant is prescribed another PERT (see [Appendix A](#) for eligible PERT). Each registry visit is anchored to the date of the previous on-site visit. There must be at least 150 days between each on-site visit unless the Early Follow-Up Visit criteria are met (see section [EARLY Follow-Up Visit](#)). Other routine clinical encounters may occur in between two registry visits, but the data collected in the Follow-Up forms should cover the time period since the last registry visit. If registry Follow-Up visits cannot occur approximately every 6 months, the site is encouraged to attempt to schedule a Follow-Up visit as soon as possible.

6.3.3 EARLY Follow-Up Visit

An EARLY Follow-up is considered any visit that occurs within fewer than 150 days from the previous visit. As stated above, an on-site visit does not qualify as Follow-Up visit if the visit occurs within fewer than 150 days since the last visit, unless the study participant is prescribed another PERT (see [Appendix A](#) for eligible PERT). When the EARLY Follow-Up criteria are met, the next follow-up visit will be calculated from the date of the Early Follow-Up visit.

6.3.4 Clinical Data Points

The following information will be collected from the study participants remotely via EDC portal every 3 months:

- Weight (current)
- Current insurance coverage and current work status
- Current OTC herbal/nutritional supplements
- Abdominal pain
- GI symptoms
- PERT use and treatment satisfaction

To limit burden on study participants, the following data will be collected from via EDC portal every 6 months:

- Dietary habits
- Health-related quality of life
- Anxiety/depression
- Healthcare utilization

The Investigator will provide the following information during the routine clinical encounters (approx. every 6 months):

- Clinical manifestations of EPI
- Current treatment(s) since last visit including medication (PERT and others) and other therapies such as nutritional support, and cognitive-behavioral therapy, as well as response to therapy
- Collection of AEs/SAEs occurring during the study (see [Medical History and AEs](#) and [SAFETY REPORTING](#) for more details).

6.4 Study Participant Exit

A study participant exits the study for one of the following reasons:

- Death
- The study participant withdraws from the study
- The study participant is being terminated by the Investigator
- The study participant transfers to a different gastroenterologist who is not a participating registry site
- The study participant is lost to follow-up (LTFU)
- The data collection period of the registry has ended

A study participant is LTFU when, despite all reasonable efforts (phone calls, email, letters, etc.), contact with the study participant cannot be reestablished, if a study participant does not complete their assessments remotely for 2 consecutive timepoints. This effort must be clearly documented by the HealthiVibe Registry Manager and information about the study participant's vital status (living or deceased) should be documented when known.

The Investigator will document the reason for the study participant's exit using the Study Participant Exit form (see [Appendix B](#)). If the reason for exit is due to death, any associated AEs, and/or AEs occurring after the last follow-up visit should be recorded and reported to HealthiVibe (see [SAFETY REPORTING](#)). The Investigator should carefully choose the option that best reflects the reason for exit at the time; the form should be completed within 5 business days of site awareness of the study participant's exit from the study.

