Study participants will be enrolled in the study if they meet eligibility criteria and after they have provided consent to participate. During the Enrollment Visit, the Investigator will confirm eligibility and will provide information on suspected/confirmed EPI diagnosis (date of diagnosis, date of onset of symptoms indicative of EPI, method of EPI diagnosis, if applicable), CP etiology, clinical manifestations of EPI (i.e., GI and nutritional manifestations), medical history (comorbidities, surgical and radiological procedures, endoscopic procedures, and laboratory abnormalities), and current treatment(s). Information collected from the study participant includes demographics, current work status, current insurance coverage, family disease history, weight/height, current over the counter (OTC) herbal/nutritional supplements, healthcare utilization, and participant-reported outcome assessments on abdominal pain, GI symptoms, health-related quality of life, depression/anxiety, and PERT use and treatment satisfaction.

Follow-Up

Follow-up data will be collected from the study participants remotely via electronic data capture (EDC) portal. Every 3 months, study participants will complete assessments on current work status, current insurance coverage, current weight, current OTC herbal/nutritional supplements, and abdominal pain, GI symptoms, and PERT use and treatment satisfaction. Every 6 months, in addition to the assessments completed every 3 months, study participants will also complete assessments on health-related quality of life, depression/anxiety, and healthcare utilization.

The Investigator will provide updates during routine clinical encounters approximately every 6 months or at least 150 days from the last registry visits. Data will be collected on clinical manifestations of EPI, current treatment(s), and active assessment of adverse events/serious adverse events (AEs/SAEs) since last visit. "Early" follow-up visits will be conducted whenever a study participant is prescribed a new PERT product. The Investigator will not complete any assessments if the study participants do not return to the sites for their expected routine clinical encounter.

Study Participant Exit

Study participants exit the study upon withdrawal from the study, lost to follow-up (LTFU), transfer of care to a different gastroenterologist, death, or any other reason resulting in a study participant's exit. The Investigator will document the reason for the exit.

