Data Collection

Study participants will be followed prospectively, and data from study participants will be collected at 3-month intervals via EDC portal. Investigators will complete assessments approximately every 6 months at the time of routine clinical encounters. AEs will be collected as part of the study data collection forms. SAEs are to be reported within 24 hours (1 business day) of awareness, whether or not the site learns of the event at the time of a registry follow-up visit.

Data Analysis

Analyses will be guided by the specific aims of the registry. Complete details of all analyses will be described in a standalone Statistical Analysis Plan (SAP) with accompanying mock Tables, Figures and Listings (TFLs). Briefly, all data will be summarized descriptively. Study disposition of all participants will be summarized including dropouts (with reasons presented for those who drop out), and for lost to follow-up (at what point they are lost, and if they return). Multivariate modeling will be employed to analyze clinical data on EPI disease history and disease progression by analyzing patterns of medical history, comorbidities, and treatment approaches. Clinical care practices will be explored with their potential impact on quality of life, comorbidities, and treatments using the same multivariate modeling. Treatment compliance will be examined for each of the models, knowing that biases are introduced with participant recall. Prescribing practices will be descriptively presented (to include type of PERT, dose at initiation and escalation, recommendation on how to take PERT, and reason for switching to another PERT, if applicable). If trends are identified in prescribing patterns, these trends may be further explored. Healthcare utilization data will be assessed with key variables from the clinical dataset.

Confounding will be assessed for predicting outcomes with the registry data. If any confounding is identified, statistical procedures may be employed as appropriate for that confounder and outcome. Given that groupings within a study population may exist, these potential grouping effects will be handled with use of ANOVA (analysis of variance) models. Data quality assessed in terms of missing data, out of range values, and completeness will be presented, as to allow for appropriate interpretation and extrapolation of the study results.

PROTOCOL SIGNATURE PAGE

Investigator Agreement

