9. SAFETY REPORTING

9.1 Adverse Events

An AE is defined as any untoward medical occurrence in a study participant administered a pharmaceutical product and which does not necessarily have to have a causal relationship with the treatment. AE data collection

begins *after* a study participant has completed an Enrollment Visit. During the Follow-Up on-site visits, the Investigator and/or designee is required to question the study participant regarding the occurrence of AEs since the previous registry visit. Pertinent details regarding any reported AEs are to be captured using the pertinent sections in the Investigator Follow-Up forms.

Any AEs that are reported by the study participant, discovered as a result of general questioning by the Investigator, should be recorded in the Investigator Follow-Up Form at the next scheduled registry visit following the onset of the event.

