9.2 Serious Adverse Events

SAEs are defined as adverse events that result in any of the following outcomes:

- Hospitalization (new or prolongation)
- Death
- Immediately life threatening (urgent intervention required to prevent outcome of death)
- Persistent/significant disability or incapacity
- Congenital abnormality or birth defect
- Otherwise serious (important medical event) in the opinion of the Investigator (i.e., event that may jeopardize the study participant and require medical or surgical intervention/treatment to prevent one of the other outcomes listed above).

SAEs are to be reported by sites in accordance with registry AE Reporting Guidelines as soon as possible after the site learns of the event (within 1 business day), via the electronic data capture system or approved backup mechanism (per the AE Reporting Guidelines). These events should also be captured by the Investigator at the next registry visit following the onset date of the event. Sites are required to request supporting documents (e.g., hospital records, laboratory results, etc.) for each SAE. These records should be submitted as soon as they become available to the site (between registry visits). The Investigator or qualified designee must remove all of the study participant's personal identifiers from the supporting documents prior to submission to HealthiVibe.

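### Non-serious AEs between the last on-site visit and exit have no prompted collection point unless the participant died

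*Protocol*

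**What the plan says.** Section 6.4 of the protocol lists six exit reasons under "A study participant exits the study for one of the following reasons": death, withdrawal, termination by the Investigator, transfer to a non-participating gastroenterologist, loss to follow-up, and end of data collection. It then gives an AE instruction for the first only: "If the reason for exit is due to death, any associated AEs, and/or AEs occurring after the last follow-up visit should be recorded".

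Elsewhere, AE collection is tied to the on-site visit:

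- **Protocol 9.1, repeated in SAP 5.7:** AEs "should be recorded in the Investigator Follow-Up Form at the next scheduled registry visit following the onset of the event".
- **Table 1 (Protocol 6.1, SAP 3.3):** the AE row is marked under on-site follow-up only, and the exit column holds only the reason for exit. The footnote reads "The Investigator will provide information about the occurrence and seriousness of AEs at Follow-up".
- **Visit spacing (Table 1 footnote):** "Every 180 days ±30 days with minimum 150 days between visits", with an exception for early visits.
- **Protocol synopsis, Follow-Up:** "The Investigator will not complete any assessments if the study participants do not return to the sites for their expected routine clinical encounter".

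Serious events have their own route. The synopsis requires SAE reports within 24 hours (1 business day) of awareness, "whether or not the site learns of the event at the time of a registry follow-up visit". Section 9.2 repeats the 1-business-day rule with no exception by exit reason.

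**The concern.** A non-serious AE is recorded at the visit after its onset. A participant who leaves has no such visit, and only a death triggers a look back over the interval.

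Take a participant who has a non-serious AE suspected to be related to PERT two months after a visit and withdraws because of it. Under section 10 the withdrawal is notified to the Investigator, and an Exit Form is completed. Nothing in that process asks about the event.

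At stake are the tables in SAP 5.7: all AEs, and AEs suspected to be related to PERT. Safety is not one of the six specific aims. Still, the protocol's Background names the effectiveness and safety of available therapies as a reason for building registries, so these counts will be read.

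**Working it through.** **Step 1. Is there any AE prompt at a non-death exit?** The possible routes, side by side:

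| Route | Where | Does it prompt for a non-serious AE after the last visit? |
|---|---|---|
| Exit instruction | Protocol 6.4 | Only if exit is by death |
| Exit column | Table 1 | No; reason for exit only |
| Exit Form | Appendix B | No AE field; free text only for termination by the Investigator |
| Next registry visit | Protocol 9.1, SAP 5.7 | Does not occur after exit |
| Clinic contact at exit | Protocol 6.3.3 | Under 150 days from the last visit it is not a Follow-Up visit unless another PERT is prescribed |
| Participant forms | Protocol 8.3 | AEs reported there must be transcribed, but the modules in 6.3.4 and Table 1 have no AE item |
| Discontinuation reasons | SAP 5.2 | No AE category |
| SAE reporting | Synopsis, Protocol 9.2 | Serious events only, and only those the site learns of |

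No row gives a prompt for a non-serious AE at a non-death exit. The participant-form route is incidental.

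**Step 2. Length of the uncovered interval.** The plan states no figure to reproduce. The interval between visits is 180 days, with a window of 150 to 210 (Table 1 footnote). Assume exits fall evenly between visits and no visit was missed before exit.

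- Mean gap = interval / 2 = 180 / 2 = 90 days.
- Over the window: 150 / 2 = 75 days to 210 / 2 = 105 days.
- Longest gap within the window: 210 days.

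A missed visit before exit lengthens the gap. A last visit that coincides with the end of data collection brings it close to 0.

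**Step 3. Person-time among early leavers.** Target enrollment is about 400 (Protocol 3.1). The documents give no early-exit rate, so assume that a proportion *d* leaves early for a reason other than death.

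Person-years uncovered = 400 × *d* × 90 / 365.25

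- *d* = 10%: 40 × 90 / 365.25 = 9.9
- *d* = 30%: 120 × 90 / 365.25 = 29.6
- *d* = 50%: 200 × 90 / 365.25 = 49.3

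**Step 4. Share of an early leaver's own follow-up.** Using months of 30.4375 days:

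- Exit at month 12: 90 / 365.25 = 24.6%
- Exit at month 24: 90 / 730.5 = 12.3%

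**The case against.** The best reply has four parts.

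**Serious events are covered.** This stands for any SAE the site learns of, whatever the exit reason. The point does not extend to those events.

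**Other sources see part of the interval.** Every 3 months participants report abdominal pain, GI symptoms, and PERT use and satisfaction, including its effect on symptoms. Section 8.3 has sites review the responses and transcribe any AE. Section 10 also has the Investigator cite the reason for withdrawal. So GI tolerability is not wholly unobserved. But none of these forms asks about AEs, and Appendix B has no field for explaining a withdrawal.

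**Tying collection to routine care is deliberate in a non-interventional registry.** That is fair for follow-up visits. It does not explain why 6.4 looks back at exit for deaths and not for others, when the site completes an Exit Form in each case. The separate AE Reporting Guidelines cited in 9.2 are not available and might add something; 9.2 cites them for SAEs.

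**Some exits cannot be repaired.** A participant lost to follow-up may be unreachable, and section 10 bars further collection if consent to future disclosure is withdrawn. Both limits belong in the fix.

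A reader might also infer three stronger claims that the documents do not support:

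- *That the loss favors the treatment.* Everyone is on PERT, there is no untreated comparator, and SAP 5.7 plans descriptive counts without a test. Under-counting is as far as the text goes.
- *That the gap can be applied to all 400 participants to give a share of total follow-up.* That would include deaths, which 6.4 covers, and end-of-collection exits, which are administrative and lose time without obvious selection.
- *That AE rates per person-time would be biased by counting time up to exit as observed.* SAP 5.7 plans numbers of patients and events, not exposure-adjusted rates.

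**Conclusion.** The concern holds in limited form. Non-serious AEs, and SAEs the site never learns of, have no prompted collection point between the last on-site visit and exit unless the participant died. All five other exit reasons are affected. The AE and PERT-related AE counts in SAP 5.7 are therefore likely too low.

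For scale, the mean gap is about 90 days per affected exit (75 to 105 across the visit window). That amounts to about 10 to 49 person-years among early leavers at an assumed early-exit rate of 10% to 50%. These figures rest on exits spread evenly between visits, no missed visit before exit, and an early-exit rate that is assumed. They measure uncovered time, not events lost.

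That events prompting a withdrawal fall in this interval is a plausible inference from timing; the documents do not say so. With descriptive safety summaries and no safety aim, this is an inexpensive improvement worth making, not a flaw that undermines the registry.

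**What to change.** Make three edits:

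1. Add an AE/SAE mark to the exit column of Table 1 in the protocol, and in the SAP's copy.
2. Extend the sentence in Protocol 6.4 so that AEs since the last follow-up visit are recorded at every exit where the participant can be contacted or the chart is available, and where consent under section 10 allows.
3. Add one AE question to the Exit Form in Appendix B, answered within the 5-business-day limit that 6.4 already sets.

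No extra visit or staff is needed. The cost is a few more minutes of site time at each exit, plus the protocol and form amendment.
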